Data Analysis. Primary analyses will be carried out on an intent-to-treat basis; additional analyses considering dropout or other observable post-randomization outcomes will make use of an instrumental-variable analysis framework. Data will be examined initially to identify issues such as departures from normality, which would suggest the need for transformations (e.g., logarithmic) and influential observations (outliers). Descriptive statistics will be computed and reported overall and by group. Demographic variables and variables characterizing the course of depression (e.g., age of onset, chronicity, number of episodes) will be screened to determine which have relationships with the outcome variables that would suggest their value as covariates. Variables that demonstrate meaningful associations with outcomes controlling for treatment group and are substantially different across groups are candidates for covariates. Demographic variables, baseline depression, and other potential covariates will be compared between the two groups to help determine if the randomization was successful in making the two groups comparable. Specific analysis plan follows below.

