Hypothesis 1. The primary outcome, namely responder/remitter status, will be compared between the esCIT+MEM and esCIT+PBO groups using chi-square statistics. Days to remission will be analyzed using the Kaplan-Meier survival method with treatment group as a stratification variable using the day on which response was observed as the event indicator. The survival function estimates the proportions achieving the response criterion, while the overall survival curve reflects speed of response. The independent variable is treatment group with two levels. A log-rank test will be used to assess the significance of any difference between treatment arms, and Cox regression to reflect the role of baseline covariates. We will also report the total time spent below the response threshold, compare summary statistics, and patterns of response within the patient over time. Analysis of change over time will be performed using linear mixed model analysis of covariance (SAS PROC MIXED). The linear mixed model permits flexible specification of the covariance structure of the repeated measures within patient, and allows analysis of incomplete cases using maximum likelihood. The outcome measures will be the HAM-D scores as well as cognitive domain scores (i.e. memory, processing speed, executive function) with the baseline rating/score on each domain as a covariate.

Hypothesis 2a. The role of brain neuroimaging biomarkers in variability of treatment response is examined in this Hypothesis. Predictor variables: We predict that baseline measures of neuroimaging biomarkers (white matter hyperintensity, regional gray or white matter volumes, hippocampal thickness and regional FDDNP binding levels) will be related to treatment outcomes. These predictions will be evaluated in the context of the models described above (i.e., general linear mixed model) by adding the posited prognostic variable as an additional predictor. Moderator variables: A limited number of exploratory analyses will be performed to evaluate possible moderators of each treatment strategy. Statistical evaluation of moderators will be done by including the posited moderator variable as an independent variable and evaluating the moderator x treatment group interaction term. Mediator Variables: We will evaluate the variable as a potential

mediator using a principal stratification framework.17,20

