Power analysis. The power analysis is focused on the primary aim of the study to assess whether the group receiving combined MEM and escitalopram demonstrate remission (HAM-D<6) compared to the other group. In the PI's pilot data, we observed remission in 83.3% of patients receiving the combination esCIT+MEM, compared to 30.7% in those receiving esCIT+PBO. In line with the message of Kraemer, et al. (2006) emphasizing that it is not safe to ignore uncertainty in pilot-study estimates of effect size, which risks underpowering the subsequent study, we derive a sample size appropriate to an effect considerably smaller than the observed difference. Specifically, we work with an assumption that the remission rate in the esCIT+MEM arm would be 70% (smaller than the observed rate of 83.3%) and that the remission rate in the esCIT+PBO arm would be 40% (larger than the observed rate of 30.7%). More involved analyses would be possible that average over a range of scenarios; the approach used here captures the essential feature that it is important to allow for possible regression to group means that are less different than those observed in the pilot study. We will draw on frameworks from the Institute of Medicine report on avoiding missing data,²² but if we recruit a total of 134 patients (67 per group) with a projected 25% dropout rate, we will be able to compare 50 completers in the esCIT+MEM group with 50 subjects in the esCIT+PBO group. Assuming that 70% of the group receiving esCIT+MEM respond versus 40% of the control subjects, the power for this chi-square test, at the 0.05 level of significance with 1 degree of freedom, exceeds 80%. To assess the impact of the proposed sample size on other analyses, we also investigated a repeated-measures analysis of our pilot data with continuous HAM-D scores as an outcome, comparing the treatment groups at 24 weeks, using the baseline measure as a covariate. We found that the effects observed in the pilot data (but reassessing with the proposed sample size) yielded a power over 0.9. In addition, we will compare the groups on the number of days until response using survival analysis. If we combine the groups and assume 40% dropout, the power of the two-sided log rank test at the 0.05 level of significance will be 0.869 with the proposed sample size.

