All severe adverse events will be reported to the subjects and to their primary physicians and the UCLA IRB/ DSMB committee within 1 week of the PI's awareness, and within 2 weeks to the NIH.

- d. If a patient demonstrates worsening of their symptoms or no response by week 8 (i.e., less than 30% improvement in HAM-D scores or CGI score of > 4) of treatment, they will be discontinued from the study and referred for appropriate clinical services.
- e. The allowed dose range for MEM will be 5-20 mg/day; escitalopram 10-20 mg/day. If patients are not able to tolerate these medications, they will be discontinued from the trial.
- f. Suicidal ideations with the HAM-D item 3 score of 3 and greater, or worsening of the score on the Beck Suicidal Ideation scale.

All dropouts will be analyzed by the reason for termination and classified as: 1. Reasons: a) Lack of efficacy; b) Side-effects; c) Lost-to-follow up; d) Hospitalization; e) Death; f) Other
2. Relation to the study drug use: a) likely; b) probable; c) unlikely.

Structural and Functional Magnetic Resonance Imaging (s- and f-MRI) Scan. The risks or discomforts associated with MRI scans may include anxiety from being in a tight, enclosed space, or discomfort from staying still for too long. Should you become anxious or agitated during the MRI scan, this research study will be immediately discontinued. The sound of the MRI scanner can be loud. We will provide earplugs to minimize the noise, but some people find the noise annoying. The tests themselves can be boring or difficult, and you may get fatigued during the scan or from the diagnostic tests.

Occasionally subjects report having a headache, feeling stiff, or feeling anxious from claustrophobia after the scan.

The magnetism of the machine attracts certain metals; therefore, people with metals in them (specifically, pacemakers, infusion pumps, aneurysm clips, metal prostheses, joints, rods, or plates) will be excluded from the study. The "metal" in dental fillings is less susceptible to magnetism and is therefore allowed. The participant will be asked about any potential sources of metal, and you pockets will be emptied prior to the study. The participant may wish to stop the study at any stage, including the testing stage. Testing will last less than 15 minutes.

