5.0 *Are there defined rules for withdrawing participants from study interventions?

Yes No

5.1 If yes, describe or indicate where the information can be found in the attached protocol.

Subjects have the right to refuse to participate or to withdraw from this research at any time without prejudice, but if they do, they will receive payment only for the time of their participation.

All patients will be carefully monitored for emergence of adverse effects. Dose of medications will be reduced, if necessary. If subjects continue to experience side effects despite dose reduction they will be discontinued from the study and alternative treatment will be recommended or appropriate professional referrals will be made. Discontinuation due to adverse events will be reported to the IRB.

All severe adverse events will be reported to the subjects and to their primary physicians and the UCLA IRB/ DSMB committee within 1 week of the PI's awareness, and within 2 weeks to the NIH.

d. If a patient demonstrates worsening of their symptoms or no response by week 8 (i.e., less than 30% improvement in HDRS scores or CGI score of > 4) of treatment, they will be discontinued from the study and referred for appropriate clinical services.

e. The allowed dose range for MEM will be 5-20 mg/day; escitalopram 10-20 mg/day. The only concomitant psychotropic medication allowed in the trial is lorazepam (1 mg or less a day). If patients are not able to tolerate these medications, they will be discontinued from the trial.

f. Suicidal ideations with the HAM-D item 3 score of 3 and greater, or worsening of the score on the Beck Suicidal Ideation scale.

All dropouts will be analyzed by the reason for termination and classified as:

1. Reasons: a) Lack of efficacy; b) Side-effects; c) Lost-to-follow up; d) Hospitalization; e) Death; f) Other
2. Relation to the study drug use: a) likely; b) probable; c) unlikely.

ID: IRB#12-001714

View: NEW 16.1 - Payment, Costs, and Injury

This view has been locked by amendment(s)

Warning: Save your work at least every 15 minutes by clicking "Save" or "Continue."

Payment, Costs, and Injury

1.0 *Indicate what the participants will receive for their participation in the study.

Check all that apply.

No payment will be provided

University check

Course Credit

Cash

Gift Cards/Bruincard Deposit

Non-Monetary Gifts or Services

Other (including vouchers for parking)

1.1 **If you selected Non-Monetary Gifts or Services or Other, describe:**

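### The days-to-remission analysis does not say how patients withdrawn by week 8 for non-response enter it; censoring them would overstate remission and, under the plan's 70% v 40%, would be expected to cost power

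*Combined protocol and SAP*

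**What the plan says.** Item d of the discontinuation list (View NEW 14.1, item 3.0, repeated in substance in View NEW 15.2, item 5.1) reads: "If a patient demonstrates worsening of their symptoms or no response by week 8 (i.e., less than 30% improvement in HAM-D scores" or a CGI score above 4), "they will be discontinued from the study and referred for appropriate clinical services".

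Hypothesis 1 (View NEW 10.1, item 6.0) says "Days to remission will be analyzed using the Kaplan-Meier survival method", adds a log-rank test and Cox regression, and interprets the result: "The survival function estimates the proportions achieving the response criterion, while the overall survival curve reflects speed of response". It states no censoring rule and no competing-event rule.

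Nearby text that bears on dropout:
- Item 6.0, Data Analysis: "Primary analyses will be carried out on an intent-to-treat basis". Additional analyses that consider dropout are to use an instrumental-variable framework.
- Item 6.0, Hypothesis 1: the linear mixed model of HAM-D and cognitive scores "allows analysis of incomplete cases using maximum likelihood".
- View NEW 14.1: "All dropouts will be analyzed by the reason for termination", with lack of efficacy among the reasons.
- Item 4.0, 8) Remission and naturalistic 6 month follow up: patients who do not remit are offered treatment outside the protocol and invited back at 6 and 12 months.
- Item 6.0, Power analysis: a reference to an Institute of Medicine report on avoiding missing data and, for the survival comparison, "assume 40% dropout, the power of the two-sided log rank test at the 0.05 level of significance will be 0.869".

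**The concern.** Kaplan-Meier, log-rank and Cox assume that a censored patient has the same later chance of the event as comparable patients still under observation. Item d selects patients for poor HAM-D response, and remission is itself a low HAM-D score. If these patients are censored at week 8, predicted non-remitters are credited with the later remission rate of those who stayed. The curve then no longer estimates the proportion that Hypothesis 1 says it does.

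Time to remission is a stated hypothesis: item 4.0, 7) Follow up assessment uses it to justify the repeated visits. If the rule stays open, it can be settled after unblinding, and the two obvious choices give different curves and different power.

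**Working it through.** **1. Does any text settle the handling?** Intent-to-treat fixes who is analysed and in which arm, not when a patient stops being at risk. The instrumental-variable work is additional and has no stated link to days to remission. The mixed model largely copes with withdrawal driven by observed HAM-D, but it estimates scores, not time to remission or the proportion remitting. Classifying dropouts by reason records why they left, not how they are analysed. The 6- and 12-month visits can give a status, possibly after outside treatment, but not a day of remission on study drug. The missing-data reference sets no rule. So nothing settles it.

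**2. The plan's own figures.** The chi-square statement reproduces: 50 v 50 at 70% v 40% gives power 0.866, or 0.815 with continuity correction, so above 80%. For the log-rank figure the plan gives no hazard, horizon or formula. With exponential times, HR = ln(0.3)/ln(0.6) = 2.357. If 134 patients with exponential dropout reaching 40% yield 60.0 events, Freedman's formula gives z = √60 × (1.357/3.357) − 1.96 = 1.17, power 0.879; Schoenfeld's gives 0.913. Removing 40% at the start (44.2 events) gives 0.767 and 0.813. The stated 0.869 is therefore plausible but its inputs are not recoverable. The text attaches it to days until response, while Hypothesis 1 speaks of both remission and response. It is not used as a benchmark here.

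**3. Closed form for censoring at week 8.** Let p be true remission, f the share of remissions that occur by week 8, and w the share of the arm withdrawn, all non-remitters. Then

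KM(24) = 1 − (1 − pf) × [1 − p(1 − f)/(1 − pf − w)].

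The values p = 0.4 and 0.7 come from the Power analysis; f and w are assumptions. With f = 1/3:
- Placebo, w = 0.25: 1 − 0.8667 × [1 − 0.2667/0.6167] = 0.508, for a true 0.40.
- Memantine, w = 0.05: 1 − 0.7667 × [1 − 0.4667/0.7167] = 0.733, for a true 0.70.

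The difference reads 22 points (0.733 − 0.508) instead of 30. If the same share of non-remitters leaves each arm, it reads 29, 27 and 21 points at 25%, 50% and 75% withdrawn.

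**4. When the direction reverses.** Keep memantine at w = 0.05. The difference stays at 30 points if placebo reads 0.433, which needs w = 0.094, a placebo/memantine ratio of 1.9. Over f = 0.1 to 0.5 and memantine w = 3% to 15% the break-even ratio is 1.61 to 2.08. For log-rank power, simulated with 25% withdrawn overall and 67 per arm:

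| Placebo/memantine ratio | Exponential timing, censored v kept | Uniform timing, censored v kept |
|---|---|---|
| 1 | 0.995 v 0.948 | 0.990 v 0.929 |
| 1.5 | 0.972 v 0.962 | 0.920 v 0.934 |
| 2 | 0.913 v 0.969 | 0.793 v 0.941 |

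Break-even is near 1.5. Non-remitters are 60% v 30% under the plan, so removing the same share of them from each arm gives a ratio of 2.

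**5. Item d applied to simulated HAM-D courses.** Assumptions: baseline mean 25, SD 4, floor 20; exponential improvement with time constant 3, 6 or 10 weeks; between-patient SD of the improvement fraction 0.2 or 0.35; individual speed fixed or varying; rating noise SD 2; the protocol's visits to week 24; remission at the first score of 6 or less; item d as under 30% improvement at week 8 without earlier remission. Arms were calibrated to 70% and 40%, with no other dropout; 1,500 trials of 67 per arm in each of 12 settings.

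| Quantity | Range over 12 settings |
|---|---|
| Withdrawn, memantine | 2–18% |
| Withdrawn, placebo | 11–39% |
| Placebo/memantine ratio | 1.9–4.7 |
| Censored Kaplan-Meier, memantine | 72–82% |
| Censored Kaplan-Meier, placebo | 43–61% |
| Censored difference | 18–29 points |
| Power, censored | 0.77–0.96 |
| Power, kept event-free | 0.95–0.98 |

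Within a setting, censoring lowered power by 1 to 19 points.

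**The case against.** The plan never says that these patients are censored; what is established is silence, and the harm is conditional on the usual execution. That is correct. But those methods, run without an instruction, end a patient's follow-up at the last observation, so the silence has a likely consequence.

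The sizes depend on assumed trajectories. Only the HAM-D trigger was modelled, not CGI or worsening, and the 12 settings were chosen, so their counts are not frequencies. At the low end the loss is about 1 point. All of this stands. The direction also depends on the withdrawal ratio: 25% withdrawn in each arm would raise the rejection rate. That is implausible for one response threshold applied to arms remitting at 70% and 40%, but it is not excluded.

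The study plan attached to View NEW 10.1, item 1.0 was not available and might contain a rule.

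A reader might infer three stronger things. First, that the plan will produce a false benefit for memantine: under its own rates the expected error is towards a smaller difference, and with both arms at 40% a similar simulation rejected in 5–6% of trials under either handling. Second, that the survival comparison falls short of its stated 0.869: the inputs and the event behind that figure are unclear, so the comparison cannot be made. Third, that the primary result is compromised: the chi-square comparison of remitter status does not use censoring.

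**Conclusion.** The concern holds as a gap in the time-to-remission analysis. No text says how patients discontinued under item d enter it, and ordinary censoring would be informative by design. That the curve would overstate remission in any arm with such leavers is firm, provided that those leaving have a lower later chance of remission than those who stay. That power would fall rests on 70% v 40% and on a placebo/memantine withdrawal ratio above about 1.5 to 2; below that the direction reverses. The 1 to 19 points, and the examples of 51% and 73%, are illustrations because the documents give no withdrawal shares. The primary chi-square test stands apart. The point should be settled before unblinding.

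**What to change.** Add to View NEW 10.1, item 6.0, Hypothesis 1:

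> For days to remission, patients discontinued under item d stay in the risk set as event-free to week 24 in the Kaplan-Meier, log-rank and Cox analyses. Only losses unrelated to response are censored. Censoring at withdrawal is a sensitivity analysis.

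Treating this withdrawal as a competing event, with cumulative incidence, Gray's test and a Fine-Gray model, is an acceptable alternative. A cause-specific log-rank or Cox model is not, because it still censors these patients.

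Three supporting changes:
- Identify these patients by a recorded item-d trigger. The dropout reason lack of efficacy is not tied to item d and may also cover other departures.
- State which other discontinuations count as unrelated to response; item f, which uses a HAM-D item, needs an explicit answer.
- Use one event term, remission or response, throughout Hypothesis 1 and the Power analysis.

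The cost is a few sentences and one recorded field. Leavers who would have remitted later count as non-remitters: in the 12 settings the kept curves read 67–71% and 38–40%, at most about 3 points low where response was slow. With heavy other dropout (40% in total) the event-free curve reads about 2 points low.

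A lesser matter: the lead-in to the discontinuation list (View NEW 14.1, item 3.0 and View NEW 15.2, item 4.1) says discontinuation is to be considered, while item d makes it definite. The sponsor should reconcile the two and say whether the 6- and 12-month invitation covers these patients. No clinical rule is proposed.
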